2.3 Blinding and Unblinding

This is only applicable for the single-blinded SCCHN Randomized Cohorts (Part 3). All other parts are open label and non-randomized, thus do not require blinding and unblinding.

Blinding of treatment assignment is critical to the integrity of this clinical study. However, in the event of a medical emergency or pregnancy in an individual subject in which knowledge of the investigational product is critical to the subject's management, the blind for that subject may be broken by the investigator. The subject's safety takes priority over any other considerations in determining if a treatment assignment should be unblinded.

Before breaking the blind of an individual subject's treatment, the investigator should determine that the unblinded information is necessary, ie, that it will alter the subject's immediate management. In many cases, particularly when the emergency is clearly not related to the investigational product, the problem may be properly managed by assuming that the subject is receiving active product. It is highly desirable that the decision to unblind treatment assignment be discussed with the Medical Monitor, but the investigator always has ultimate authority for the decision to unblind. The Principal Investigator should only call in for emergency unblinding AFTER the decision to discontinue the subject has been made.

For this study, the method of unblinding for emergency purposes is the Interactive Response Technology (IRT). In cases of accidental unblinding, contact the Medical Monitor and ensure every attempt is made to preserve the blind. Any request to unblind a subject for non-emergency purposes should be discussed with the Medical Monitor. In case of an emergency, the investigator(s) has unrestricted access to randomization information via the IRT and is capable of breaking the blind through the IRT system without prior approval from the Sponsor. Following the unblinding, the investigator shall notify the Medical Monitor and/or study director.

For information on how to unblind for emergency, please consult the IRT manual.

The subjects, investigator, and site staff will be blinded to the study drug administered (lirilumab in combination with nivolumab or nivolumab monotherapy). For all subjects in the SCCHN Randomized Cohorts (Part 3), and the Signal Detection in SCCHN with Lirilumab, Nivolumab, and Ipilimumab Combination (Part 5), each investigative site must assign an unblinded

pharmacist/designee and an unblinded site monitor will be assigned by sponsor to provide oversight of drug supply and other unblinded study documentation.

2.4 **Protocol Amendments**

This analysis plan reflects all protocol amendments through Amendment 12, dated 08-May-2018.

2.5 Data Monitoring Committee

For all parts of the study, a blinded independent review committee will review all available tumor assessment scans to determine response using RECIST v1.1 criteria. When required, adjudicated events will be submitted to health authorities for review on a specified timeframe in accordance with the adjudication documentation.

3 OBJECTIVES

3.1 **Primary Objective**

3.1.1 Primary Objective for the Dose Escalation and Cohort Expansion (Part 1; Completed) and the SCCHN Cohort Expansion (Part 2; Completed)

The Dose Escalation and Cohort Expansion (Part 1): To assess the safety and tolerability of lirilumab given in combination with nivolumab and to identify DLTs and the MTD of the combination in subjects with advanced (metastatic and/or unresectable) solid tumors.

The SCCHN Cohort Expansion (Part 2): To assess the safety and preliminary anti-tumor activity of the combination of lirilumab and nivolumab in subjects with advanced solid tumors.

3.1.2 Primary Objective for the SCCHN Randomized Cohorts (Part 3 - closed to enrollment)

To estimate the ORR of lirilumab given in combination with nivolumab in subjects with recurrent or metastatic SCCHN that has relapsed or progressed within 6 months of the last dose of a platinum-containing therapy and whose tumors express PD-L1.

3.1.3 Primary Objective for the Signal Detection Cohort Expansion (Part 4)

Removed with Revised Protocol 12.

3.1.4 Primary Objective for the Signal Detection in SCCHN with Lirilumab, Nivolumab, and Ipilimumab Combination (Part 5 - closed to enrollment)

To assess the safety and preliminary anti-tumor activity of the combination of lirilumab with nivolumab and ipilimumab in subjects with platinum-refractory recurrent or metastatic SCCHN.

3.1.5 Primary Objective for the Signal Detection in Previously Untreated MEL with Lirilumab, Nivolumab, and Ipilimumab Combination (Part 6)

Removed with Revised Protocol 12.

3.2 Secondary Objectives

3.2.1 Secondary Objectives for the Dose Escalation and Cohort Expansion (Part 1; Completed) and the SCCHN Cohort Expansion (Part 2; Completed)

The secondary objectives are as follows:

- To characterize the PK of lirilumab and nivolumab when co-administered.
- To monitor immunogenicity of lirilumab and nivolumab when administered as combination therapy.
- To assess the pharmacodynamic effect in tumor tissue on TIL subsets from MEL and SCCHN subjects treated with lirilumab given in combination with nivolumab.

3.2.2 Secondary Objectives for the SCCHN Randomized Cohorts (Part 3 - closed to enrollment)

The secondary objectives are as follows:

- To estimate disease control rate (DCR), DOR, and time to response of lirilumab given in combination with nivolumab.
- To assess depth of response of lirilumab given in combination with nivolumab and of nivolumab monotherapy.
- To assess the OS of lirilumab given in combination with nivolumab and nivolumab monotherapy.
- To assess the PFS of lirilumab given in combination with nivolumab and nivolumab monotherapy.
- To estimate the ORR by investigator assessment of lirilumab given in combination with nivolumab and nivolumab monotherapy.
- To assess the safety of lirilumab given in combination with nivolumab in subjects with SCCHN.

3.2.3 Secondary Objectives for the Signal Detection Cohort Expansion (Part 4)

Removed with Revised Protocol 12.

3.2.4 Secondary Objectives for the Signal Detection in SCCHN with Lirilumab, Nivolumab, and Ipilimumab Combination (Part 5 - closed to enrollment)

The secondary objective is as follows:

- To estimate DOR of lirilumab given in combination with nivolumab and ipilimumab.
- To assess depth of response of lirilumab given in combination with nivolumab and ipilimumab.
- To characterize the PK and immunogenicity of lirilumab in combination with nivolumab and ipilimumab.
- To investigate the immunomodulatory properties of lirilumab in combination with nivolumab and ipilimumab, and to evaluate potential baseline and on-treatment biomarkers in peripheral

blood and tumor for association with efficacy in subjects with platinum-refractory recurrent or metastatic SCCHN.

• To explore biomarkers of lirilumab in combination with nivolumab and ipilimumab as therapy in all subjects with platinum-refractory recurrent or metastatic SCCHN.

3.2.5 Secondary Objectives for the Signal Detection in Previously Untreated MEL with Lirilumab, Nivolumab, and Ipilimumab Combination (Part 6)

Removed with Revised Protocol 12.

4 ENDPOINTS

4.1 Primary Endpoints

Safety and preliminary anti-tumor activity are the primary objective for all parts (i.e. Parts 1, 2, 3, and 5) except Part 1, where the primary objective is to assess the safety and tolerability of lirilumab given in combination with nivolumab, and Part 3, where the primary objective is to assess estimate the objective response rate of lirilumab given in combination with nivolumab.

For safety objective, all subjects who receive at least 1 dose of study drug will be evaluated for safety as measured by the incidence of AEs, SAEs, AEs leading to discontinuation, and deaths assessed during treatment and for 150 days in follow-up. In addition, clinical laboratory test abnormalities will be examined.

All non-serious AEs will be collected from Day 1 until 150 days after the subject's last dose of study drug or until they discontinue the study as per study protocol Section 3.5 and all SAEs must be collected from the date of the subject's written consent until 150 days after discontinuation of dosing or until they discontinue the study as per study protocol Section 3.5. AEs will be categorized

using the most current version of MedDRA. AEs and laboratory values will be graded according to the National Cancer Institute (NCI) Common Terminology Criteria for Adverse Events (CTCAE) version 4.03.

For preliminary-antitumor activity, the primary endpoint will be to estimate ORR by derived BORs per RECIST v1.1 using investigator-provided tumor assessments for all Parts. The BORs for investigator-assessed responses per RECIST v1.1 for Parts 3 and 5 will be listed. Details regarding the definition of ORR will be given in the upcoming Secondary endpoint section for preliminary antitumor activity.

4.2 Secondary Endpoints

4.2.1 Preliminary Antitumor Activity

The following set of study-level efficacy endpoints will be used for comprehensive assessment of antitumor activity.

4.2.1.1 Objective Response Rate (ORR)

ORR is defined as the total number of participants whose best overall response (BOR) is either a complete response (CR) or partial response (PR) divided by the total number of participants in the population of interest. BOR for a participant will be **derived** using investigator-provided tumor measurements per RECIST v1.1 for all Parts. BOR for a participant will also be assessed by the investigator per RECIST v1.1 for Parts 3 and Part 5. All summaries or listings of BOR will be using derived BOR per RECIST v1.1 for all Parts.

BOR for a participant is defined as the best response designation recorded between the date of first dose (or date of randomization) and the date of first objectively documented progression per RECIST v1.1 or the date of subsequent therapy, whichever occurs first. CR or PR determinations included in the BOR assessment must be confirmed by a second scan no less than 4 weeks after the criteria for response are first met. For participants without documented progression or subsequent therapy, all available response designations will contribute to the BOR assessment. For participants who continue treatment beyond progression or begin subsequent therapy, the BOR should be determined based on response designations recorded up to the time of the initial RECIST v1.1 defined progression or subsequent therapy, whichever occurs first.

4.2.1.2 Median Time to Response (mTTR)

The objective response will be further characterized by the time to response. TTR for a participant with a confirmed BOR of CR or PR is defined as the time from the first dosing date to the date of the first documented objective response (CR or PR). TTR will only be evaluated in participants with a BOR of CR or PR.

4.2.1.3 Median Duration of Response (mDOR)

The significance of ORR is assessed by its magnitude and duration of response. DOR for a participant with confirmed response is defined as the time from the date of first response (CR or PR) to the date of first objectively documented tumor progression as determined using RECIST v1.1 or death due to any cause, whichever occurs first. Participant who remain alive and

have not progressed will be censored on the date of their last evaluable tumor assessment. Participants who started subsequent anticancer therapy without a prior reported progression will be censored at the last evaluable tumor assessment prior to initiation of the subsequent anticancer therapy. Response duration will only be evaluated in participants with a confirmed BOR of CR or PR.

4.2.1.4 Progression Free Survival Rate (PFSR)

The PFSR is defined as the proportion of treated participants remaining progression free and surviving at time T (eg, 24 weeks) since the first dosing date. The proportion will be calculated by the K-M estimate which takes into account censored data.

PFS for a participant is defined as the time from the first dosing date to the date of first objectively documented disease progression or death due to any cause, whichever occurs first. Clinical deterioration in the absence of radiographic evidence is not considered progression for the purpose of determining PFS. Participants who died without a reported prior progression will be considered to have progressed on the date of their death. Participants who remained alive and have not progressed will be censored on the last evaluable tumor assessment date. Participants who started subsequent therapy without a prior reported progression will be censored at the last evaluable tumor assessment prior to initiation of the subsequent anticancer therapy. Participants who did not have any post-baseline tumor assessment and did not die will be censored on the date of first dose of study medication.

Situation	Date of Progression or Censoring	Outcome
No baseline tumor assessment	First dosing date	Censored
No on-study tumor assessments and no death	First dosing date	Censored
Documented progression	Date of first documented progression per RECIST v1.1 (excludes clinical progression)	Progressed
No progression and no death	Date of last evaluable tumor assessment	Censored
New anticancer therapy, tumor- directed radiotherapy, or tumor- directed surgery received without progression reported prior or on the same day	Date of last evaluable tumor assessment prior to the date of initiation of subsequent anticancer therapy	Censored
Death without progression	Date of death	Progressed

Table 4.2.1.4-1:Censoring Scheme for PFS

General Efficacy Endpoints Definitions:

Best overall response (BOR) for a subject is the best response designation over the study as a whole, recorded between the date of first dose of study medication and the date of objectively documented progression per RECIST 1.1 or the date of subsequent anti-cancer therapy, whichever occurs first, in the study. For subjects without documented progression per RECIST 1.1 or

subsequent anti-cancer therapy, all available response designations will contribute to the BOR determination. For subjects who continue treatment beyond progression, the BOR should be determined based on response designations recorded up to the time of the initial RECIST 1.1-defined progression. Additionally, the following will be applicable for BOR evaluation:

- For a BOR of complete response (CR) or partial response (PR), the response assessment must have been confirmed by a consecutive assessment no less than 4 weeks (28 days) later.
- For a BOR of stable disease (SD), the minimum criteria for SD duration (e.g, 6-8 weeks) must have been satisfied (42 days will be used to derive SD). This time minimum criteria only applies to derived BOR of SD, not to per timepoint evaluation.

Duration of response (DOR) for a subject with confirmed response is defined as the time from first response (CR or PR) to the date of the first documented tumor progression as determined using RECIST 1.1 criteria or death due to any cause, whichever occurs first. Subjects who remain alive and have not progressed will be censored on the date of their last tumor assessment (prior to subsequent cancer therapy). Response duration will only be evaluated in subjects with objective response of CR or PR.

Time to response (TTR) for a subject is defined as the time from date of first dose of study medication to the date of the first documented objective response (CR or PR). Time to response will only be evaluated in subjects with objective response of CR or PR.

Progression-free survival (PFS) for a subject is defined as the time from the date of first dose of study medication to the date of first documented disease progression or death due to any cause, if death occurred within 100 days after last lirilumab or nivolumab dose of study drug. Clinical deterioration in the absence of radiographic evidence is not considered progression for the purpose of determining PFS. Subjects who remain alive and have not progressed will be censored on the last tumor assessment date (prior to subsequent cancer therapy). Subjects who did not have any on study tumor assessment and did not die will be censored on the date of first dose of study medication.

Overall survival (OS) for a subject is defined as the time from date of first dose of study medication to the date of death for any cause. A subject who has not died will be censored at last known date alive. OS for a subject who initiated new cancer treatment, will also be censored at the date of the new treatment initiation.

The efficacy endpoints that will used to evaluate BOR, PFS, and OS include:

- Objective response rate (ORR): The proportion of subjects with BOR of either a CR or PR in the population of interest (all treated patients or response evaluable patients).
- Disease control rate (DCR): The proportion of subjects with BOR of either a CR, PR, or SD in the population of interest (all treated patients or response evaluable patients).
- Median duration of response (mDOR)
- Median time to response (mTTR)

- Median overall survival (mOS)
- Median progression-free survival (mPFS)
- Progression-free survival rate (PFSR) at Month 3, 6, and 12: The proportion of subjects remaining progression free and surviving at 3, 6, 9, and 12 months (conditional on availability of a minimum number of subjects with sufficient follow-up) calculated by the product-limit method (Kaplan-Meier estimate)
- Overall survival rate (OSR) at Month 6, 12, 18, 24, and 36: The proportion of subjects surviving at month 6, 12, 18, 24, and 36 (conditional on availability of a minimum number of subjects with sufficient follow-up) calculated by the product-limit method (Kaplan-Meier estimate)

Disease assessment with CT and/or MRI, as appropriate, will be performed at baseline and every 8 weeks (Q8W and Q12W for subjects in the Signal Detection in Previously Untreated MEL with Lirilumab, Nivolumab, and Ipilimumab Combination [Part 6]) until confirmed disease progression, at the completion of follow-up, or until subjects withdraw from the study. Disease assessments at other timepoints may be performed if the investigator is concerned about tumor progression. Tumor responses will be derived for appropriate populations of subjects as defined by RECIST v1.1²² (see Appendix 3 of the protocol) from tumor measurements. For the Dose Escalation and Cohort Expansion (Part 1; completed) and the SCCHN Cohort Expansion (Part 2; completed), investigator-assessed responses and treatment decisions related to subject management will be based on irRECIST⁹ (see Appendix 2 of the protocol); all other study parts will use only RECIST v1.1. All radiographic assessments performed for study purposes will be submitted to the third-party radiology vendor for central review. Tumor assessments should be submitted to the third-party radiology vendor as they are performed on an ongoing basis. At the time of investigator-assessed disease progression, the site must request a BICR from the thirdparty radiology vendor. For details on the timelines and associated process requirements refer to the imaging manual.

Changes in tumor measurements and tumor responses will be assessed by the investigator using irRECIST criteria. Investigators will also report the number and size of new lesions that appear while on-study. The timepoint tumor assessments will be reported on the CRF based on investigators' assessment using irRECIST criteria. The SCCHN Randomized Cohorts (Part 3), the Signal Detection Cohort Expansion (Part 4),

however, will use only

RECIST v1.1 for all assessments. Please refer to Appendix 3 of the protocol for specifics of RECIST v1.1 and Appendix 2 of the protocol for specifics of irRECIST criteria to be utilized in this study.

The SCCHN Randomized Cohorts (Part 3)

The primary endpoint is ORR based on assessment in all subjects randomized to lirilumab plus nivolumab.

The secondary efficacy endpoints of the SCCHN Randomized Cohorts (Part 3) are DCR, DOR, time to response, depth of response, OS, PFS, ORR by investigator (in subjects randomized to

Statistical Analysis Plan	CA223001
BMS-986015	lirilumab

nivolumab monotherapy), and ORR according to investigator-assessed response. All randomized subjects will be monitored by radiographic assessment Q8W (\pm 7 days) beginning from the first dose date until Week 48 and Q12W (\pm 7 days) thereafter until PD or treatment discontinuation (whichever occurs later), to determine changes in tumor size. Tumor progression or response endpoints will be assessed by investigator using RECIST v1.1 criteria.

The Signal Detection Cohort Expansion (Part 4)

Removed with Revised Protocol 12.

The Signal Detection in Previously Untreated MEL with Lirilumab, Nivolumab, and Ipilimumab Combination (Part 6)

Removed with Revised Protocol 12.

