8.3 Endpoint Definitions

Endpoints are defined as follows.

Safety Endpoint Definitions

Safety is the primary endpoint in this study except for the SCCHN Randomized Cohorts (Part 3). All subjects who receive at least 1 dose of study drug will be evaluated for safety as measured by the occurrence of AEs, SAEs, deaths, and laboratory abnormalities, assessed during treatment and for 150 days in follow-up.

Study level endpoints used to assess the safety objective will be based on AE reports and the results of vital sign measurements, ECGs, physical examinations, imaging studies, and clinical laboratory tests. AEs will be categorized using the most current version of MedDRA; both AEs and laboratory tests will be graded using NCI CTCAE v4.03. All subjects who receive study drug therapy will be evaluated for safety as measured by the rate of AEs, and SAEs, and will be assessed during treatment and for 150 days in follow-up.

Safety will be measured by the following:

- Incidence of AEs: all non-serious AEs will be collected from Day 1 until 150 days after the subject's last dose of study drug or until they discontinue the study as per [Section 3.5](#) and all SAEs must be collected from the date of the subject's written consent until 150 days after discontinuation of dosing or until they discontinue the study as per [Section 3.5](#).
- Incidence of clinical laboratory test abnormalities including hematology and serum chemistry, and thyroid panel abnormalities, assessed at specified timepoints as designated in the Time and Events Section ([5.1](#)).

Efficacy Endpoint Definitions

Study level endpoints used to assess the anti-tumor activity objective are defined as follows:

ORR is defined as the total number of subjects whose BOR is either CR or PR divided by the total number of subjects in the population of interest.

PFS rate is defined as the probability of a subject remaining progression-free and surviving to 24 weeks. The probability will be computed based on the number of days between the first dose of study drug and PD or death, as defined by each criterion. For those subjects who remain alive and have not progressed, PFS will be censored on the date of the last tumor assessment. The above will be calculated based on tumor measurements occurring Q8W during treatment and at planned timepoints during the clinical follow-up period.

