BOR is the best response designation recorded from the start of the study treatment until the end of treatment taking into account any requirement for confirmation, based on RECIST v1.1 criteria. CR or PR determinations included in the BOR assessment must be confirmed by a consecutive second (confirmatory) evaluation meeting the criteria for response that is performed at least 4 weeks after the criteria for response are first met. The above will be determined based on tumor measurements occurring Q8W (\pm 7days) during the treatment period (or Q6W (\pm 7days) for 1 year [48 weeks] and Q12W (\pm 7days) afterwards for the Signal Detection in SCCHN with Lirilumab, Nivolumab, and Ipilimumab Combination [Part 5] and once during the clinical follow-up period.

Other efficacy endpoints include the following:

OS is defined as the time from randomization to the date of death. A subject who has not died will be censored at last known date alive. OS will be followed continuously while subjects are on the study drug and every 3 months for up to 3 years following the first dose of study drug via in-person or phone contact after subjects discontinue the study drug.

PFS is defined as the time from randomization to the date of the first documented tumor progression (per RECIST v1.1). Subjects who die without a reported prior progression will be considered to have progressed on the date of their death. Subjects who did not progress or die will be censored on the date of their last evaluable tumor assessment. Subjects who did not have any on-study tumor assessments and did not die will be censored on the date they were randomized. Subjects who started any subsequent anti-cancer therapy without a prior reported progression will be censored at the last evaluable tumor assessment prior to initiation of the subsequent anti-cancer therapy.

DOR is defined as the time between the date of first confirmed response to the date of the first documented tumor progression (per RECIST 1.1), or death due to any cause, whichever occurs first. Subjects who neither progress nor die will be censored on the date of their last evaluable tumor assessment. Subjects who started any subsequent anti-cancer therapy without a prior reported progression will be censored at the last evaluable tumor assessment prior to or on initiation of the subsequent anti-cancer therapy. DOR will be evaluated for responders (confirmed CR or PR) only.

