6 STUDY PERIODS, TREATMENT REGIMENS AND POPULATIONS FOR ANALYSES

6.1 Study Periods

This study consists of 3 periods: pre-treatment, on-treatment, and post-treatment/follow-up period.

The pre-treatment period covers from the time of signing of the informed consent form to prior to the first dose of study medication.

The on-treatment period starts at the time of the first dose of study medication and extends to the time of decision to discontinue a subject from study therapy or when the subject completes therapy per protocol.

The post-treatment clinical follow-up period begins the day after the on-treatment period ends and extends to up to 150 days after the last dose of lirilumab or nivolumab or ipilimumab, as long as the patients are still enrolled in the study.

Additional follow-up for survival outcomes may extend to up to 3 years after initiation of study drug.

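### SAP 4.2.1.4 defines PFS twice: one definition counts every death without progression, the other only deaths within 100 days of the last dose, with no rule for later deaths

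*SAP*

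**What the plan says.** **SAP 4.2.1.4, opening definition.** PFS runs from first dose to the "date of first objectively documented disease progression or death due to any cause, whichever occurs first". The text adds: "Participants who died without a reported prior progression will be considered to have progressed on the date of their death". Table 4.2.1.4-1 has a row for death without progression; the outcome is an event on the date of death.

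**SAP 4.2.1.4, General Efficacy Endpoints Definitions.** PFS is defined again, also from first dose, to documented progression or "death due to any cause, if death occurred within 100 days after last lirilumab or nivolumab dose of study drug". The censoring rules that follow cover two groups. One is "Subjects who remain alive and have not progressed will be censored on the last tumor assessment date (prior to subsequent cancer therapy". The other is subjects with no on-study scan who did not die.

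**Protocol 8.3.** The PFS definition states: "Subjects who die without a reported prior progression will be considered to have progressed on the date of their death". The PFS rate uses the "number of days between the first dose of study drug and PD or death, as defined by each criterion". Neither has a time limit on death.

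**Follow-up.** Under SAP 6.1, clinical follow-up "extends to up to 150 days after the last dose of lirilumab or nivolumab or ipilimumab". It also says: "Additional follow-up for survival outcomes may extend to up to 3 years after initiation of study drug". Protocol 3.7 stops survival collection with Revised Protocol 12.

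**Use.** SAP 7.5 calls for the Kaplan-Meier PFS curve and median, and the endpoint list in 4.2.1.4 adds rates at 3, 6, 9 and 12 months. SAP 7.1 combines Parts 1 and 2 and puts Parts 3 and 5 in listings only.

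**The concern.** Two analysts following this SAP could produce different PFS curves from the same data. A subject who stops treatment without RECIST progression and dies 120 days after the last dose is an event under the opening definition. Under the general definition that subject is not an event and has no censoring date, so the programmer has to invent a rule.

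This is more than a missing detail. The general definition states a rule that takes known deaths out of an endpoint in which death is a component. Those deaths are not a random subset: both PFS definitions say that clinical deterioration without radiographic evidence is not progression, so subjects who deteriorate, stop and die later are among those affected. Censoring them is informative.

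The clause also conflicts with neighbouring rules. Both duration-of-response definitions in the SAP count death from any cause with no window, so the same death could end a response and yet not count for PFS. SAP 7.6.2 summarises deaths up to 150 days after the last dose, so a death on days 101 to 150 would be in the death table and absent from PFS.

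**Working it through.** The documents give no PFS assumption, event count or power, so there is no planned figure to reproduce. The check has two parts.

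**1. The texts side by side, for a death without prior progression or new therapy**

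| Source | Death up to 100 days after last dose | Death after 100 days |
|---|---|---|
| SAP 4.2.1.4, opening definition and Table 4.2.1.4-1 | Event at death | Event at death |
| Protocol 8.3 | Event at death | Event at death |
| SAP 4.2.1.4, general definition | Event at death | Not an event; no censoring date |

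The conflict is confined to the last cell.

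**2. What the general definition would do to the estimates**

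Kaplan-Meier curves were simulated for 40,000 subjects, with late deaths as events and then as censored. None of these assumptions comes from the documents except the scan intervals:
- underlying median PFS 90, 120 or 180 days (exponential), with progression seen at 8-weekly scans;
- 2%, 5% or 10% of subjects dying 101 to 365 days after the last dose without progression or new therapy;
- last dose on days 1 to 168;
- four possible censoring dates, since the SAP gives none. The continued-scan case follows Protocol Table 5.1.1-3: a scan at the day-100 visit, then every 12 weeks.

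Change in PFS rate in percentage points (late deaths censored minus late deaths as events), range over all nine combinations:

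| Censoring date | 3 months | 6 months | 9 months | 12 months |
|---|---|---|---|---|
| Date of death | 0.0 | +0.1 to +0.7 | +0.6 to +3.0 | +0.7 to +5.0 |
| Last scan, day 100 then every 12 weeks | 0.0 | +0.1 to +0.5 | +0.4 to +2.6 | +0.5 to +4.2 |
| Day-100 scan, none later | 0.0 | -0.7 to 0.0 | 0.0 to +1.3 | -0.5 to +1.9 |
| Last on-treatment scan, none later | -2.2 to -0.3 | -6.1 to -0.7 | -4.6 to -0.4 | -2.5 to 0.0 |

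The median changed by at most 1 day in every case.

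Two features follow from the structure:
- *The 3-month rate cannot rise.* An excluded death is more than 100 days after the last dose, hence more than 100 days after the first, so it lies beyond 3 months (about 91 days). Removing it changes nothing before that point. Earlier censoring can only leave the estimate alone or lower it.
- *The sign can reverse.* A subject whose late death counts as an event stays in the risk set, event-free, until death. Censored at an early scan, the subject leaves the risk set before other subjects' events, and each of those then weighs more.

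**The case against.** The strongest reply is that Table 4.2.1.4-1 is the SAP's only situation-by-situation rule, and it treats death without progression as an event. An analyst would probably follow the table, and then no bias arises. The clause may be leftover text: Protocol Amendment 12 added the 150-day follow-up, and SAP 7.6.7 and 7.6.8 still mix 100 and 150 days. That origin is an inference. It is a fair reply on likelihood, but no text gives the table precedence or labels the 100-day version as a sensitivity analysis, so the contradiction stands.

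The number of affected subjects is also limited. Those who start new therapy are censored at an earlier assessment under both definitions. Table 5.1.1-3 keeps scanning non-progressors off treatment, so many would have progression recorded before death. Survival collection stopped with Revised Protocol 12. These points reduce the size of the effect but do not settle which definition applies.

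Three stronger readings are tempting, and the documents do not support them.
- *That PFS is overstated.* This requires the general definition to be the one programmed, and a censoring date that pushes the estimate up. Neither is stated.
- *That a sizeable share of the cohort is lost.* A reader might take the 7.5-month median OS for nivolumab in Protocol 1.1.2, obtain 2^(-(100/30.4)/7.5) = 0.74 surviving past 100 days, and multiply by an assumed 5% to 20% stopping without progression: 0.74 x 5% = 3.7% and 0.74 x 20% = 14.8%. That is a ceiling on reclassified subjects, not a change in PFS. It needs every one of them to die, with the death recorded and no progression or new therapy first. It also applies a head-and-neck figure, from treatment stop, to five tumour types.
- *That the finding of no differential signal against nivolumab is affected.* Protocol Section 1 lists median PFS among the parameters reviewed, but nothing shows that the review used the 100-day wording, and the median barely moves.

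**Conclusion.** The contradiction is certain on the text: SAP 4.2.1.4 conflicts with itself, and its general definition conflicts with Protocol 8.3. The general definition is also incomplete, because a death after day 100 has neither an event nor a censoring rule.

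The consequence is conditional and modest. If the 100-day version is programmed, the expected effect under the protocol's scan schedule is somewhat higher PFS rates at 6, 9 and 12 months. The size rests wholly on the assumed frequency of late deaths, the assumed dosing times and the chosen censoring date. If scanning in practice ended with treatment and late deaths were censored at the last on-treatment scan, the rates would instead be lower, including at 3 months.

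This should be fixed, but it does not threaten the trial's main conclusions. PFS is not a primary endpoint in any part and carries no formal test. Protocol 8.3.2 names it as a secondary endpoint only for Part 3, whose results are listed rather than summarised.

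**What to change.** In SAP 4.2.1.4, under General Efficacy Endpoints Definitions, delete the condition on the timing of death (everything after the first comma in "death due to any cause, if death occurred within 100 days after last lirilumab or nivolumab dose of study drug"). Then replace the rest of that PFS paragraph with a reference to the opening definition and Table 4.2.1.4-1. Deleting the clause alone would leave two paragraphs that still differ: only the opening one has a rule for a missing baseline assessment and requires the last scan to be evaluable.

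Keep first dose as the time origin, as both SAP definitions do. Protocol 8.3 starts PFS at randomization but its PFS rate at first dose, and Parts 1 and 2 are not randomized; a sentence in the SAP should acknowledge this.

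If the sponsor wants a 100-day version, label it a sensitivity analysis and state the censoring date for later deaths.

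The cost is a short text edit with no new data collection. Deaths not collected after survival follow-up ended cannot be recovered, but those on record can be used. The downside is that reported PFS at 6 to 12 months may look slightly less favourable than under the 100-day rule.
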